#### **10.3.5 Treatment effects on cross-sectional binary variables**

Binary endpoints such as the cross-sectional “responder status” at a visit will be analysed using SAS PROC GENMOD with logit as the link function for the responder probability. An unstructured correlation matrix will be used as working correlation matrix if technically possible, alternatively an autoregressive, a compound-symmetry, or if necessary, an independent working correlation matrix will be used. The systematic effects will include visit and treatment-by-visit interaction as factors and will be adjusted for the  $\log_2$ -transformed number of nocturnal voids at baseline-RT, subtracted by 1, as a covariate interacting with visit number. Odds ratios relative to placebo with associated 95% confidence intervals (without multiplicity adjustment) will be presented. The analyses will be applied to the observed data for the ITT-RT analysis set. Combinations of visit and dose of FE 201836 where all or none of the subjects respond will be omitted from the analysis since this corresponds to estimates of infinity in a logistic regression model.

For the investigation of interaction with sex, combinations of sex, visit and dose of FE 201836 where all or none of the subjects respond will be omitted from the analyses, and an autoregressive correlation matrix will be used, if technically possible, alternatively, a compound-symmetry, or if necessary, an independent working correlation matrix will be used.

In the analysis of the responder variable corresponding to one nocturnal void decrease from baseline, only subjects with at least one nocturnal void at baseline will be included. In the analysis of the responder variable corresponding to two nocturnal voids decrease from baseline, only subjects with at least two nocturnal voids at baseline will be included. In the analysis of the responder variable corresponding to three nocturnal voids decrease from baseline, only subjects with at least three nocturnal voids at baseline will be included.

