3.1 Timing of Interim Analyses

The first interim will occur after 125 subjects have enrolled into the trial. This includes 50 subjects to the control (d_0), 50 to the highest dose of FE 201836 (d_6), and 25 subjects on the active comparator (d_{AC}). Subsequent interims will be conducted every 8 weeks and will continue beyond full accrual while the enrolled subjects are completing the 12 weeks of follow-up. Because interims are defined by calendar time, the total number of planned interims, I , is random and will depend on the rate at which subjects accrue to the trial.

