### 3.1.2 Sample Size

A maximum of 300 subjects (males and females) will be randomized into the trial. The sample size was based on computer simulations under five sigmoidal dose-response profiles without baseline adjustment. The operating characteristics and associated power were estimated for the different dose-response scenarios by computer simulations using the Fixed and Adaptive Clinical Trial Simulator (FACTS) version 5.6.

The average number of subjects and probabilities for futility and success are presented in Table 2.

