In addition to the illustrations of the therapeutic window specified in the protocol, illustrations of the therapeutic window will be produced using the estimated treatment contrast compared to placebo for the change from baseline-RT to lowest post-baseline measurement of serum sodium as the safety indicator. The inclusion of desmopressin in the plots illustrating the therapeutic window (“Corresponding efficacy and safety of desmopressin will be illustrated in a side panel for comparison.”) has been deleted to comply with “None of the primary, secondary or explorative analyses will include desmopressin.” (Section 10.1).

In the analyses of time to ‘confirmed’ hyponatraemia episodes, the time to event is defined as the time of confirmation in stead of the time to first measurement below the threshold to avoid conditioning on the future. The protocol states “The associated relative hazards of treatment and gender will be analysed using Cox proportional hazards model adjusting for baseline serum sodium and age (<65,  $\geq$ 65 years). Possible heterogeneity between the genders in the relative treatment hazards will be explored by the inclusion of a treatment-by-gender interaction term”. These analyses will not be performed since the trial is too small to perform Cox regression analyses of the occurrence of hyponatraemia events with 9 treatment groups and 2 covariates.

The adverse events tables presenting incidences of least 5% have been changed to presenting at incidences of at least 10% because it is expected that for several of the FE 201836 treatment groups, 20 subjects or less are allocated to the group.

According to [REDACTED], the interim analyses will deviate from the Appendix 2 in the protocol regarding the derivation of the allocation probabilities by the factor  $1/(n_d + 1)$  before the normalization to sum to 1.

Remaining changes are all considered clarifications of presentations specified in the protocol.

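### SAP 10.3.5 omits responder cells with 0% or 100% response and gives no substitute estimate, so whether an odds ratio is reported depends on its own result

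*SAP*

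**What the plan says.** SAP 10.3.5 analyses by-visit responder status with a repeated logistic model (GEE) on observed data. On the mean model it says: "The systematic effects will include visit and treatment-by-visit interaction as factors", with log2 baseline voids interacting with visit. It then says: "Combinations of visit and dose of FE 201836 where all or none of the subjects respond will be omitted from the analysis", giving as reason "since this corresponds to estimates of infinity in a logistic regression model". The next paragraph of the same section, on differences between men and women, carries a parallel rule: "combinations of sex, visit and dose of FE 201836 where all or none of the subjects respond will be omitted from the analyses".

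No other estimate is named for an omitted cell. Both sentences name FE 201836 doses only, so a placebo cell with no responders, or only responders, is not covered.

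The protocol's description of this analysis (Section 9.7.3) contains no omission. SAP Section 14 quotes that description and restates it as clarified, again without the omission. The same section expects that "for several of the FE 201836 treatment groups, 20 subjects or less are allocated to the group".

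**The concern.** Two doses with the same true response rate can be treated differently by chance: the one with a single responder gets an odds ratio, and the one with none gets nothing. The same happens at the other end, where a dose at which everyone responds disappears. An infinite maximum-likelihood estimate is a reason to change the estimator for that cell. It does not mean the cell is uninformative.

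At stake is how complete and balanced the odds-ratio tables are for small dose groups. The conditions for empty or full cells are present:

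- several groups of 20 or fewer;
- about half of each sex (Protocol 4.1), so sex-specific cells of about 10 or fewer in those groups;
- thresholds up to 100% reduction and 3 voids;
- for the 3-void analysis, restriction to subjects with at least three baseline voids.

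**Working it through.** The documents state no responder rate, power or sample size for these analyses, so there is no figure to reproduce.

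**Inputs from the documents.** Several FE 201836 groups where "20 subjects or less are allocated to the group" (SAP 14). Maximum 300 randomised (SAP 3.1.2). Of the first 125 subjects, 50 on placebo (Protocol Appendix 2, Section 3.1), then 2 in 10 (Protocol 3.3). Placebo at full size is 50 + 0.2 × (300 − 125) = 85. **Assumed:** every true rate p, every exact cell size n, and independent subjects within a cell.

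**Step 1. How often a cell is omitted, and what the kept cells look like.**

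- P(omitted) = (1 − p)^n + p^n
- Mean retained rate r = (p − p^n) / (1 − (1 − p)^n − p^n)
- Odds factor = [r/(1 − r)] / [p/(1 − p)]

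For n = 20, p = 0.05: 0.95^20 = 0.3585; r = 0.05/0.6415 = 0.0779; factor = (0.0779/0.9221)/(0.05/0.95) = 1.61.

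| n | p | omitted | r | odds factor |
|---|---|---|---|---|
| 20 | 0.05 | 36% | 0.078 | 1.61 |
| 20 | 0.10 | 12% | 0.114 | 1.16 |
| 20 | 0.20 | 1.2% | 0.202 | 1.01 |
| 20 | 0.30 | 0.08% | 0.300 | 1.00 |
| 20 | 0.70 | 0.08% | 0.700 | 1.00 |
| 20 | 0.90 | 12% | 0.886 | 0.86 |
| 20 | 0.95 | 36% | 0.922 | 0.62 |
| 12 | 0.05 | 54% | 0.109 | 2.3 |
| 10 | 0.05 | 60% | 0.125 | 2.70 |
| 10 | 0.20 | 11% | 0.224 | 1.16 |
| 8 | 0.20 | 17% | 0.240 | 1.3 |
| 6 | 0.20 | 26% | 0.271 | 1.5 |

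The factor is taken at the mean retained rate. Averaging the log odds of the retained cells instead gives smaller values at low rates: 1.45 at n = 20, p = 0.05, and 1.01 at n = 20, p = 0.10.

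**Step 2. Effect on the other cells.** Each dose-by-visit combination has its own parameter. In a degenerate cell the fitted probability goes to 0 or 1 and the residuals go to zero, so under an independence working correlation the cell adds nothing to the other score equations. In simulated fits with the SAP mean structure and about 7 of 24 cells degenerate, omitting rather than keeping them changed the remaining log odds ratios by at most 1.3 × 10⁻¹⁵. Under an exchangeable correlation the median change was under 0.001, but many fits that kept the cells did not converge, so that result is only indicative. The SAP's first choice, unstructured, was not tested.

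**Step 3. What an omitted cell could have shown.** Exact conditional 95% intervals for the odds ratio against an assumed placebo cell of 85, with the add-0.5 point estimate:

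| dose | placebo | exact 95% CI | add-0.5 odds ratio |
|---|---|---|---|
| 0/15 | 26/85 | 0 to 0.70 | 0.07 |
| 0/15 | 13/85 | 0 to 1.80 | 0.17 |
| 0/15 | 4/85 | 0 to 8.91 | 0.58 |
| 15/15 | 60/85 | 1.35 to infinity | 13.1 |

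The first and last rows exclude 1, in opposite directions, and the GEE table would show neither.

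**Step 4. Placebo.** At an assumed true rate of 2%, the chance of no placebo responder at a visit is 0.98^85 = 18%. Every odds ratio against placebo at that visit is then without a finite estimate, and the SAP gives no instruction.

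**The case against.** The rule is prespecified, its stated reason is correct, and no success criterion, futility decision, MED or ED85 uses these analyses. The 50% endpoint has two safeguards. The Bayesian responder analysis (SAP 10.3.3) gives an odds ratio for every dose without this rule, and SAP 10.5 plans frequency tables by treatment and visit for both 50% responder definitions, so an empty cell stays visible. All of this stands, and it confines the point to the exploratory thresholds, for which 10.5 specifies no such tables, and to the by-sex analyses.

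A reader might infer three stronger things that the documents do not support:

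- **That the remaining odds ratios are inflated.** The treatment-by-visit model gives each cell its own parameter, and Step 2 found no such inflation. The factors in Step 1 describe selection across repeated trials.
- **That the worst results are removed.** The rule is symmetric and removes 100% cells as well; the selection runs downward when response is common.
- **That the responder dose-response curve is flattened.** That curve comes from the Bayesian model. The GEE fits no curve.

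It can also be said that Section 14 ends by treating all remaining changes as clarifications of presentation. That general sentence does not tell a reader that estimates will be withheld according to their result.

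**Conclusion.** The point holds as one of selective reporting in secondary and exploratory output. The primary analysis is untouched. Cells are omitted on their observed outcome, nothing replaces them, a degenerate placebo cell is not addressed, and Section 14 does not list the rule.

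The size depends on rates and cell sizes that the documents do not give. At n = 20 it is negligible for rates of about 20% to 80%. At 5% or 95%, about a third of cells would be omitted, with odds factors of 1.61 and 0.62. In sex-specific cells of 6 to 8, a true rate of 20% would already lose 17% to 26% of cells. The practical exposure is therefore the 90% and 100% reduction and 3-void thresholds, and the sex-interaction analyses, in the small dose groups. The placebo figure of 85 assumes that the trial reaches 300 subjects.

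**What to change.** In SAP 10.3.5, replace both omission sentences with a rule along these lines:

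- Keep the GEE for all non-degenerate cells.
- For each cell with 0% or 100% responders, report the count and denominator. Add either an exact or Firth-type odds ratio with its interval, or a risk difference with an exact or score interval, against placebo at that visit.
- Apply the same rule when the placebo cell is degenerate.

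In SAP 10.5, extend the frequency tables by treatment and visit to all responder thresholds and add them by sex. List the rule in Section 14.

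The cost is a wording change, a little standard code and more tables. The drawback is that degenerate cells would use a per-visit estimator while the rest use the repeated-measures GEE, so the tables should mark which method produced each estimate.

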#### 10.3.6 Treatment effects on single-time-point quantitative variables

Treatment effects on single-time-point quantitative variables will be analysed using SAS PROC MIXED to perform an ANCOVA (a non-parametric dose-response curve is assumed). For the percentages of nights with response, the systematic effects will comprise treatment as a categorical variable and baseline-RT number of nocturnal voids minus 2 as a linear covariate. For change from baseline-RT in copeptin, the systematic effects will comprise treatment as a categorical variable and the baseline-RT level minus 13.1 as a linear covariate. For change from baseline-RT to lowest observed serum sodium, the systematic effects will comprise treatment as a categorical variable and the baseline-RT level minus 135 as a linear covariate. The treatment contrasts (with associated 95% confidence intervals without multiplicity adjustment) versus placebo will be tabulated and graphically illustrated. The analyses will be applied to the observed data on the ITT-RT analysis set. For change from baseline-RT to lowest observed serum sodium, the analyses will be performed both using randomized treatment for the observed data on the ITT-RT analysis set for comparability with the results for the efficacy variables and using actual treatment for the Safety-RT analysis set for comparability with the analyses of episodes of hyponatraemia based on observed serum sodium.

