9.10.3.1 Hyponatraemia during the Randomised Treatment Period

These analyses are restricted to the Safety Analysis Set only.

The incidence of the post-baseline worst-case hyponataemia episode for each subject will be summarised as described in [Table 9-6](#).

Graphs will plot the serum sodium levels by treatment group and the profiles of the subjects who at any time (Visit 1 and onwards) have a serum sodium level <135 mmol/L will be highlighted.

Kaplan-Meier plots of time from randomisation (Visit 4) to hyponatraemic serum sodium levels (<135, <130 and ≤125 mmol/L) per treatment group will be produced. For the thresholds <135 and <130 mmol/L at least 3 and 2 consecutive observations, respectively, have to be below the threshold to yield a hyponatraemic event ([Table 9-6](#)). For both cases the time is from randomisation until first observation below the respective limit that counts.

The associated relative hazards of treatment and gender will be analysed using Cox proportional hazards model adjusting for baseline serum sodium and age (<65, ≥65 years). Possible heterogeneity between the genders in the relative treatment hazards will be explored by the inclusion of a treatment-by-gender interaction term.

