Lowest observed change from baseline-RT in Serum Sodium				Alternative safety indicator for therapeutic window	
Incidence and severity of Adverse Events	Section 11.3.1				
Adverse Event of Special Interest: Hyponatraemia Episodes	Section 11.2.1				
Clinically significant changes in laboratory values and vital signs	Sections 11.3.2 and 11.3.3				

a Endpoint assessed at Weeks 1, 4, 8 and 12.

b Endpoints are derived using all diary data collected during the treatment period.

c Endpoint assessed at Weeks 1 and 12.

d Correlation between changes in FUSP and total sleep time at Weeks 1, 4, 8 and 12.

e This questionnaire is retrospective and raw scores will be used in the analysis (not changes from baseline) and the ANCOVA model will not be adjusted for baseline value.

f Endpoint assessed at Weeks 4, 8 and 12.

g Correlation with NPI at Visit 2.

h Endpoint assessed at Week 12.

Illustration of the therapeutic window is described separately in Section 10.4 and safety related endpoints are further described in Section 11.

Explorative analyses by sex are planned for all endpoints, including correlation analyses. For these the following are noted:

- Estimates of the sex-specific dose-response for the aggregated averages after 12 weeks of treatment will follow the Bayesian analysis described in Sections 10.2.1 and 10.3.3 by conducting a separate analysis for each sex. Possible differences between the sex-specific models will be investigated.
- The regression models will be supplemented with an analysis considering sex as well as all interactions between sex and the effects specified in the all-subjects analysis, including any interaction terms specified in the all-subject analysis. Possible differences between the treatment effects for men and women will be evaluated by the treatment-by-visit-by-sex (treatment-by-sex for single-visit outcomes) interaction term with the effect of treatment-by-visit (treatment for single-visit outcomes) included in the model.

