#### 10.4 The therapeutic Window

The estimated sigmoidal dose-response curve with 95% credibility limits compared to placebo (left-sided y-axis) will be illustrated together with the incidence per 100 person-weeks with 95% confidence limits of observation of serum sodium  $<130$  mmol/L and  $\leq 125$  mmol/L, respectively, at or before 12 weeks (both on the right-sided y-axis). The estimated treatment effects with 95% confidence limits compared to placebo for the groups treated with FE 201836 based on the MMRM model described in Section 10.3.4 will also be presented in the graph. The horizontal x-axis will represent the dose range of FE 201836. The therapeutic window is defined as the dose range where FE 201836 is deemed efficacious while the incidence of hyponatraemia is acceptable. Two illustrations will be made with different estimated dose-response curves for the efficacy of FE 201836: one using the results from the primary analysis and one using Sensitivity Analysis 6 based on the actual treatment received.

The sex-specific therapeutic windows will be illustrated similarly.

The therapeutic window of nocturnal volume will be presented similarly.

In addition, similar illustrations of the therapeutic window will be produced using the estimated treatment contrast compared to placebo for the change from baseline-ENR to lowest post-baseline measurement of serum sodium as the safety indicator. To make the results for the efficacy indicator

and the safety indicator comparable in each of these figures, the same treatment definition and the same analysis set will be used for both indicators in each figure.

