For all baseline-adjusted analyses of more than one visit at a time, the interaction between visit and baseline has been added as a systematic effect. This is done because it is unlikely that the baseline value has the exact same influence on measurements 1 week after baseline and 12 weeks after baseline. Furthermore, this leads to a frequentist approach more similar to the Bayesian model in which the association with baseline depends on the visit. For all analyses estimating the interaction between treatment and sex, interactions have been added between sex and each of the systematic

effects. This is done to prevent potentially contradictory results from separate analyses of the two sexes and the evaluation of the interaction between treatment and sex (overall or visit-specific, as appropriate) caused by non-comparable statistical models.

The protocol states in Section 9.7.3 Secondary and Exploratory Analyses:

Binary endpoints such as “responder status” at a certain visit will be analysed using SAS PROC GENMOD with the logit as link function for the responder probability. An unstructured covariance matrix will be assumed for the repeated responder status which will be adjusted for baseline value as covariate and treatment, visit and treatment-by-visit interaction as factors. (Associated with e.g., responder analysis in terms of reduction in number of voids, cumulative distribution function plots of percentage change from baseline by treatment may be produced.)

This has been clarified to the following:

Binary endpoints such as the cross-sectional “responder status” at a visit will be analysed using SAS PROC GENMOD with logit as the link function for the responder probability. An unstructured correlation matrix will be used as working correlation matrix. The systematic effects will include treatment, visit, and treatment-by-visit interaction as factors, and will be adjusted for the  $\log_2$ -transformed number of nocturnal voids at baseline-RT, subtracted by 1, as a covariate interacting with treatment. Odds ratios relative to placebo with associated 95% confidence intervals (without multiplicity adjustment) will be presented. The analyses will be applied to the observed data for the ITT-RT analysis set.

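### SAP 10.4 should measure the supplementary lowest-sodium indicator from the randomisation baseline; adding age to the ANCOVA behind it is a cheap, optional refinement

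*SAP*

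**What the plan says.** Protocol 9.10.3.1 planned a "Cox proportional hazards model adjusting for baseline serum sodium and age", with age split at 65 years. SAP 14 drops it openly: "These analyses will not be performed since the trial is too small to perform Cox regression analyses of the occurrence of hyponatraemia events".

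The SAP adds a different analysis, an ANCOVA of one continuous value per subject. Table 5 lists it as "Lowest observed change from baseline-RT in Serum Sodium", an alternative safety indicator for the therapeutic window. SAP 10.3.6 gives the model, again with baseline-RT as the starting point: "lowest observed serum sodium, the systematic effects will comprise treatment as a categorical variable and the baseline-RT level minus 135 as a linear covariate". It is run on both ITT-RT and Safety-RT, and the contrasts "versus placebo will be tabulated and graphically illustrated". SAP 10.3.1 adds a sex analysis: "The regression models will be supplemented with an analysis considering sex as well as all interactions between sex". Section 14 explains that "interactions have been added between sex and each of the systematic" effects. Age is in neither version.

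SAP 10.4 then describes the extra figures as using the contrast for "change from baseline-ENR to lowest post-baseline measurement of serum sodium as the safety indicator". Section 14, describing the same figures, says baseline-RT.

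**The concern.** There are two points, and the first is the firmer.

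**Baseline.** SAP 6.1.1 takes baseline-ENR from data up to Visit 2 and baseline-RT from data up to Visit 4. The active run-in and the washout lie between them. The choice therefore decides whether values measured on 500 µg before randomisation can count as post-baseline. SAP 13 bases the risk-benefit assessment on the therapeutic-window figures, so a sodium contrast that mixes run-in drug exposure into the placebo arm would weaken a safety display.

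**Age.** Protocol 1.1 names age as a risk factor for hyponatraemia in pooled desmopressin trials, and the protocol chose it as an adjuster. The new model keeps baseline sodium and omits age without giving a reason. The small-trial reason in SAP 14 concerns a model of events, so it does not carry over to a continuous outcome. What is at stake is precision in dose arms that SAP 14 expects, in several cases, to hold 20 subjects or fewer.

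**Working it through.** **Baseline wording, side by side**

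- SAP 10.3.6, Table 5 and section 14: baseline-RT. SAP 10.4: baseline-ENR.
- Serum sodium is scheduled at Visits 1, 3, 5, 6, 7 and 8 (protocol 7.1.3.1), and at Visit 4 with the standard laboratory tests (SAP Table 3, footnote b). Visit 3 ends the run-in, and its sample is meant to be taken while the subject is on drug.
- Taken from baseline-ENR, the post-baseline values include Visit 3. Taken from baseline-RT, they do not.
- Screening requires at least 135 mmol/L. At Visit 3 only a confirmed value below 130 excludes. A subject who enters at 135 and falls to 130 in the run-in can still be randomised to placebo. The literal 10.4 definition scores that subject at 130 − 135 = −5 mmol/L or lower before any placebo is taken.
- For a subject randomised to 500 µg, Visit 3 is one more value on the same dose. For a placebo subject it is the only value on drug. The expected effect is to pull the contrast towards zero. The documents give no sodium distribution, so its size cannot be computed.

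**Degrees of freedom for the age term**

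- Stage 1: 125 × (2, 2, 1)/5 = 50, 50, 25, which matches protocol Appendix 2, section 3.1.
- Stage 2 at the maximum of 300: 175 × (2, 7, 1)/10 = 35, 122.5, 17.5.
- Placebo: 50 + 35 = 85. FE 201836: 50 + 122.5 = 172.5. Desmopressin: 42.5, left out following SAP 10.1. ANCOVA N = 257.5.
- Residual df = 257.5 − 7 groups − 1 covariate = 249.5; with age, 248.5.
- Sex version: 14 treatment-by-sex means + 2 baseline slopes = 16 parameters, so 241.5 df; with age and age-by-sex, 239.5. If age is unrelated, the cost is √(241.5/239.5) − 1 = 0.4%.

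**Precision**

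Assumptions, none of them in the documents: age 65 or over lowers the nadir by b mmol/L; a share p of subjects is 65 or over; SD is the residual SD without age. The variance share of age is f = p(1−p)b²/SD², and the SE falls by 1 − √(1−f). With the same age effect in every arm:

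| p | b | SD 2.5 | SD 3 | SD 3.5 |
|---|---|---|---|---|
| 0.5 | 1 | 2.0% | 1.4% | 1.0% |
| 0.5 | 2 | 8.3% | 5.7% | 4.2% |
| 0.3 | 1 | 1.7% | 1.2% | 0.9% |
| 0.3 | 2 | 7.0% | 4.8% | 3.5% |

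Simulation includes the lost df and chance imbalance in age (4,000 runs; assumed arms of 85, 72, 20, 20, 20, 20 and 21; a 20-subject arm against placebo). The mean fall is 0.6% (p 0.3, b 1, SD 3.5) to 8.2% (p 0.5, b 2, SD 2.5). At p 0.5 and SD 3:

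- uniform b = 0.5: about 0.2%; b = 1: 1.2%; b = 2: 5.6%
- effect on active drug only: about 0.4% for b = 1 and about 2% for b = 2
- no age effect: a rise of 0.2% (5th to 95th percentile −0.4% to +0.9%)

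The active-only figures are smaller because the common age slope is diluted to about b × 172.5/257.5 = 0.67b. For b = 1, f = 0.25 × 0.67²/9 = 0.0125, a fall of 0.6% before the 0.2% cost, or about 0.4% net.

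In absolute terms, for 20 against 85 subjects with SD 3, the 95% half-width is 1.9695 × 3 × √(1/20 + 1/85) = 1.47 mmol/L. With a uniform effect and p 0.5 it becomes 1.45 (b = 1) or 1.38 (b = 2).

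**The case against.** The case against the age term is strong, and most of it stands. The size of the gain rests wholly on assumptions. In a middle case the half-width moves by 0.02 mmol/L, which would not change how a figure is read. The protocol's evidence on age comes from desmopressin, whereas FE 201836 is described as short-acting with little unchanged renal excretion. Screening and the run-in remove the most susceptible subjects before randomisation, which may shrink any age effect. The model follows the treatment-plus-baseline pattern used throughout 10.3.6, and SAP 11.2.1.2 already plots lowest sodium against age. Splitting age at 65 also discards information. What survives is that the cost is negligible and the variable is the protocol's own.

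A reader might infer that the SAP dropped a promised age adjustment. It did not: the Cox model was withdrawn openly with a fair reason, and the protocol set no covariates for this ANCOVA. A reader might also infer that the contrasts are biased. Randomisation prevents systematic bias. A change in age mix between stages could unbalance pooled placebo against the later doses, but the documents show no such change.

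On 10.4, the fair reply is that three other places say baseline-RT, so the programmers may well do the right thing. That makes it a likely slip, and one worth removing.

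**Conclusion.** Both points hold as small corrections to a supplementary indicator.

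The 10.4 mismatch is a genuine inconsistency with a plausible direction of harm, dilution of the dose-placebo sodium contrasts. Its size is unknown. The documents do not support reading it as a deliberate second analysis, because section 14 describes the same figures from baseline-RT.

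The age term is optional. Its expected benefit runs from about 0.2% (uniform 0.5 mmol/L effect) through 0.4% to 2% (1 to 2 mmol/L, active drug only) to 0.6% to 8% (1 to 2 mmol/L in all arms), against a cost of about 0.2% if age is unrelated. An age coefficient would describe an association across arms; it would not show drug-specific risk in older subjects. The primary result and the main therapeutic window, which uses incidence of sodium below 130 and at or below 125 mmol/L, are unaffected by either change.

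**What to change.** 1. In SAP 10.4, replace baseline-ENR with baseline-RT for this indicator, and state that only post-randomisation sodium values count towards the lowest value. Cost: one word and a short clause.
2. Optionally, in SAP 10.3.6, add age (<65, ≥65 years) as a factor for change from baseline-RT to lowest sodium, in both the ITT-RT and Safety-RT runs. In the sex version include age and age-by-sex, as the section 14 rule on sex interactions implies. Use the same adjusted contrasts in the tables, the graphs and the 10.4 figures. If the age coefficient is reported, give it with a 95% confidence interval and label it an association.

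The second change costs 1 df (2 in the sex version). No new data are needed, since date of birth is collected at screening (protocol 7.2.1).
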